5.1.2. Pooling Sites for Analysis

Data from all investigational sites will be pooled for the analysis, unless specified otherwise.

5.1.3. Handling of Missing Data

Best efforts will be utilized to minimize missing values. If a subject discontinues study treatment early, the subject will be asked to complete study assessments at ET/safety follow up visit.

For the analysis of both continuous and categorical data, summary statistics will be computed based on observed data. Since the duration of treatment period varies in Part B, efficacy endpoints by visit will be summarized through 12 months during Part B. Additional summaries beyond 12 months may be computed depending on the enrollment pattern, i.e., the number of subjects attending visits after the Week 77 visit. AE endpoints by visit will be summarized through LPLV in Part B.

For a QOL endpoint, in the event of missing data, the total score will be estimated according to the provision for missing domains in the calculation algorithm of the score. For example, if a subject has missing data in FACIT-F questionnaire at a visit, the prorated FACIT-F score will be calculated if more than 50% of the items (a minimum of 7 out of 13 items) are available. Otherwise, the score is missing.

For the analysis of AEs and concomitant medications/procedures, if the start/stop date of an AE/concomitant medication/procedure is missing or partial, the corresponding study day will be left blank. However, inferences will be made from the partial and missing dates to classify medications as prior and/or concomitant and AEs as treatment emergent or not treatment emergent. These inferences are described in [Section 8.1](#).

5.2. Data Summaries

5.2.1. Continuous Variables

Continuous variables will be summarized using descriptive statistics including the number of non-missing values (n), mean, standard deviation (SD), median, minimum, and maximum.

Where specified in the table shells, the 25th and 75th percentiles will also be provided. Means, medians, and the 25th and 75th percentiles will be presented to one decimal place beyond that with which the data were captured. SDs will be presented to two decimal places beyond that with which the data were captured. Minimum and maximum will be displayed to the same number of decimal places as that with which the data were captured.

Unless impractical within a given table, statistics will be aligned by the decimal place (or assumed decimal place) in the summary tables.

5.2.2. Categorical Variables

Categorical variables will be summarized by counts and percentages. All percentages will be rounded to one decimal place. The percentage will be suppressed when the count is zero. Unless specified otherwise, the denominator for all percentages will be the number of subjects with non-missing data for a given summarization. This number (n) will be included with categorical summaries unless the same variable is also being summarized with descriptive statistics, in which case 'n' will already be provided.

5.2.3. Time-to-Event Variables

Time-to-event variables will be summarized using Kaplan-Meier estimate over time, along with median time to event and probability of an event at specific time points. Additionally, a Kaplan-Meier plot over time will be constructed. Partial dates will not be imputed, hence considered unknown. In general, for subjects who do not experience the event, the time-to-event will be censored at the study day of last assessment within the study period.

6. STUDY SUBJECTS

6.1. Disposition of Subjects

Subject disposition will be summarized including the number of subjects in FAS, Safety Analysis Set, PK Analysis Set, and PD Analysis Set. The number of subjects with the status of completed Part B and discontinued Part B early, including the primary reason for those who discontinued, will be tabulated for all subjects enrolled in Part B.

Subject disposition, including the date of the last visit and the reason for early termination for subjects who did not complete the study treatment, will be provided in a data listing.

6.2. Demography and Baseline Disease Characteristics

Demographics and baseline disease characteristics will be summarized for FAS.

6.2.1. Demography

Demographic characteristics including age (years), age category (<65, ≥65), gender, race, ethnicity, country, geographic location, height (cm), weight (kg), weight category (<75 kg, ≥75 kg), and body mass index (kg/m²) will be summarized. Geographic locations are defined as follows:

- Europe includes Austria, Germany, Italy, United Kingdom, and Norway.
- North America includes the United States.
- Asia includes Japan.
- Other includes Australia and New Zealand.

6.3. Protocol Deviations

All protocol deviations will be recorded throughout the study. Major and minor protocol deviations/violations are to be pre-specified prior to database lock. All major protocol deviations will be summarized for FAS. All deviations occurring in Part B, both major and minor, will be provided in a data listing.

6.4. Non-study Drug Medications

6.4.1. Concomitant Medications

Concomitant medications within Part B are those administered on or after the Part B start date. Concomitant medications will be coded using World Health Organization drug enhanced dictionary (March 2018 version or higher) and will be summarized using FAS.

Separate tables will be generated to summarize the concomitant CAD medical treatment(s) and protocol prohibited CAD treatment(s) (both determined via medical adjudication).

Additionally, all concomitant medications taken during Part B will be provided in a data listing.

6.4.2. Non-drug treatments and procedures

Non-drug treatments and procedures administered during Part B (whether for CAD or other condition), excluding transfusions, will be summarized for FAS and listed.

6.5. Study Drug

Study drug exposure will be summarized using Safety Analysis Set. Subject-level information on dosing with study drug during Part B will also be provided in a data listing.

6.5.1. Exposure

Study drug exposure, measured by the duration of study treatment, the number of BIVV009 administrations and total actual BIVV009 dose, will be summarized by study period for the Safety Analysis Set.

The duration of the study treatment (in weeks) is calculated as follows:

1. Combined Study Period: $(\text{date of last dose} - \text{date of first dose in Part A} + 15)/7$
2. Part B Study Period: $(\text{date of last dose} - \text{Part B start date} + 15)/7$

The actual dose administered at each visit is calculated as:

$$\text{Total volume administered} / \text{Total volume prepared} * \text{assigned dose.}$$

The total BIVV009 dose will be summarized as follows:

1. Combined Study Period: The summation of all actual doses administered in Parts A and B.
2. Part B Study Period: The summation of all actual doses administered in Part B, alone.

7. EFFICACY ANALYSIS

7.1. General Efficacy Principles

Unless specified otherwise, all analyses described will be performed using FAS and will include summaries (see [Section 5.2](#)) and listings only. No formal hypothesis will be tested with regards to efficacy endpoints.

Additionally, all efficacy data will be provided in data listings.

7.2. Analysis of Efficacy Endpoints (Part B Study Period)

All analyses described below will be performed on the Part B Study Period, starting at Week 27.

7.2.1. Continuous Endpoints

The continuous endpoints include:

- LDH
- Haptoglobin
- Reticulocyte count

The above endpoints will be summarized by visit, including change from baseline, starting at Week 27, and will continue through the Week 77 visit. All change from baseline tables will also include a summary of Baseline statistics and individual summary statistics will follow those presented in [Section 5.2.1](#). For patients with more than 12 months of follow-up in Part B, all endpoints at the Week 79 visit and beyond will be provided in a data listing.

7.2.2. Categorical Endpoints

The categorical endpoints include:

- Incidence of solicited symptomatic anemia
- Incidence of other CAD-related symptoms

The above endpoints will be summarized by visit descriptively using the FAS and will be based on the observed data starting at Week 27, continuing through the Week 77 visit. Baseline summaries will be included for comparative purposes. For patients with more than 12 months of follow-up in Part B, observed data at the Week 79 visit and beyond will be provided in the listings.

Additionally, the following endpoints will be summarized using all data in Part B (including data from the Week 79 visit and beyond):

- Incidence of thromboembolic events

- Incidence of hemolytic breakthrough

7.2.3. Endpoints Based on Patient-reported Outcomes

The patient-reported outcome (PRO) endpoints are as follows:

- Continuous Endpoints
 - FACIT-Fatigue score
 - EQ-5D index score
 - EQ-5D-5L visual analogue scale
 - SF-12 physical component score (PCS) and mental component score (MCS)
 - SF-12 sub-scale scores
- Categorical Endpoints
 - Patient's Global Impression of Change (PGIC)
 - Patient's Global Impression of [Fatigue] Severity (PGIS)
 - EQ-5D-5L Descriptive System

Details of the above PRO instruments and algorithms for deriving the scores can be found in the Part A SAP. For continuous variables, the overall score and its change from baseline will be summarized descriptively for each time point, starting at Week 27 and continuing through the Week 77 visit based on the FAS.

PGIC and PGIS will be summarized as ordinal variables by visit for the FAS, starting at Week 27 and continuing through the Week 77 visit.

When applicable missing items will be handled based on the specific PRO instrument. Subjects missing baseline evaluations would not be included in the PRO analyses. For patients with more than 12 months of follow-up in Part B, observed data at the Week 79 visit and beyond will be provided in the listings.

7.2.4. Healthcare Resource Utilization

The number of healthcare visits by type (office visit, hospital ER visit, hospitalization, and ICU stay) will be collected and presented in a listing.

7.3. Analysis of Efficacy Endpoints (Combined Study Period)

All analyses below will be conducted on the FAS for the Combined Study Period starting at Baseline/Day 0.

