4 INVESTIGATIONAL PLAN

4.1 STUDY DESIGN

This open-label, single-arm study is designed to evaluate the efficacy, safety, and tolerability of BIVV009 in patients with the complement-mediated disorder, primary CAgD, who have a recent history of blood transfusion.

During the 6-week Screening/Observation Period, prospective patients will have a detailed medical history documented (including transfusion history of ≥ 6 months), physical evaluations for screening, and blood samples collected on 3 occasions approximately every 2 weeks.

Patients may receive a transfusion(s) during the Screening/Observation Period prior to the first study drug infusion if medically indicated per the Investigator's discretion. However, the baseline visit (and first infusion of study drug) must occur at least 7 days following the transfusion.

Part A

The study will enroll approximately 20 primary CAgD patients who have a recent history of transfusion, defined as at least 1 transfusion during the last 6 months prior to enrollment. Eligible patients will receive an IV infusion of BIVV009 over approximately 60 minutes on Day 0, Day 7, and every 14 days thereafter through Week 25 (ie, Days 21, 35, 49, 63, 77, 91, 105, 119, 133, 147, 161, and 175). Patients who miss a dose (ie, outside the dosing window or >17 days since last dose) should return to the site for an unscheduled visit 1 week prior to the next scheduled dose in order to receive an additional loading dose. Patients will have an End-of-Treatment (EOT) visit on Day 182 (Week 26).

Patients who meet the transfusion criteria in [Table 1](#) during the 6-month treatment period will receive a transfusion. Patients who receive a transfusion during Part A will not be withdrawn from the study and will be eligible to participate in Part B.

Table 1 - Transfusion criteria

A patient will receive a transfusion during Part A or Part B if his or her Hgb level meets either of the following criteria:

- Hgb is <9 g/dL and the patient is symptomatic, *or*
- Hgb is <7 g/dL and the patient is asymptomatic

A responder analysis will be conducted following completion of the EOT visit at Week 26. The responder definition is provided in [Table 2](#).

Table 2 - Responder definition

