A patient will be considered a responder in Part A if he or she did not receive a blood transfusion from Week 5 through Week 26 (EOT) and did not receive treatment for CAgD beyond what is permitted per protocol. Additionally, the patient's Hgb level must meet either of the following criteria:

- Hgb level is ≥ 12 g/dL at the treatment assessment endpoint (defined as mean value from Weeks 23, 25, and 26), *or*
- Hgb increased ≥ 2 g/dL from baseline (defined as the last Hgb value before administration of the first dose of study drug) at treatment assessment endpoint

Note: Any patient withdrawing from the study after Week 5 and prior to the Week 23 visit will be considered a non-responder.

A list of excluded concomitant medications, as well as allowed concomitant medications with restrictions, is provided in [Section 6.2.6](#). Beyond the permitted concomitant medications, study drug, and transfusions, patients may receive no other therapies for the treatment of CAgD while enrolled in this study; patients requiring other treatment for their CAgD in Part A will be withdrawn from the study and counted as non-responders. These patients will not be eligible to participate in Part B.

Part B

Following completion of dosing in the 6-month treatment period, patients will continue to receive BIVV009 dosing during Part B, the long-term safety and durability of response extension phase. Part B will run for 2 years following last patient out (LPO) under Part A. Patients requiring treatment with permitted concomitant medications and/or transfusions will not be discontinued from the study. Patients in Part B will be transfused per the Transfusion Criteria in [Table 1](#). Patients who receive a transfusion during Part B will not be withdrawn from the study.

Patients will be dosed with BIVV009 every 2 weeks, as in Part A. Should patients deviate from their scheduled dosing, a repeat loading dose may be required. On-site visits will be completed ~ every 3 months (at a minimum) for collection of PK, PD and ADA samples during the 1st year of treatment in Part B, then every 6 months and for additional safety and efficacy measures.

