5.3 REMOVAL OF PATIENTS FROM STUDY PARTICIPATION, AND STUDY SUSPENSION AND STOPPING RULES

Patients will be informed that they are free to withdraw from the study at any time and for any reason. Patients should inform the site of withdrawal in writing. The Investigator (or designee) may remove a patient from the study if, in the Investigator's (or designee's) opinion, it is not in the best interest of the patient to continue the study. Patients may be withdrawn due to the following:

- Change in compliance with inclusion/exclusion criteria that is clinically relevant and affects patient safety.
- Occurrence of AEs that, in the opinion of the Investigator, may jeopardize patient safety or data integrity. This includes clinically significant hematologic breakthrough events attributable to the development of ADA and/or the development of positive SLE auto-antibody titers.
- Occurrence of pregnancy in patient while receiving study drug.
- Intake of non-permitted concomitant medication that might affect patient safety or study assessments/objectives.
- Clinical signs of SLE or any other immune complex disease.

The Investigator will immediately notify the Sponsor's Study Monitor of all patients who withdraw from treatment. In case of withdrawal, all ET assessments should be performed as applicable ([Section 6.1.4](#)). The date the patient is withdrawn from the study and the reason for withdrawal will be recorded on the patient's electronic Case Report Form (eCRF). All withdrawn patients will be followed until resolution of all their AEs or until the unresolved AEs are judged by the Investigator (or designee) to have stabilized. Patients who withdraw from study early (prior to Week 5) may be replaced at the discretion of the Sponsor. Patients who withdraw from study after Week 5 and prior to Week 23 will not be eligible to participate in Part B.

The entire study may be discontinued at the discretion of the Sponsor based on the occurrence of the following:

- Adverse events unknown to date or increased frequency and/or severity, and/or duration of known AEs
- Results of the interim analysis ([Section 7.9](#)) demonstrating absence of clinically significant increases in Hgb
- Medical or ethical reasons affecting the continued performance of the study
- Difficulties in the recruitment of patients
- Cancellation of or change in drug development program per the discretion of the Sponsor

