3.1.1. Study Sample

Patients in Part B will be a subset of the patients enrolled in Part A. All patients who complete Part A, including those receiving transfusions, will be eligible for Part B. Patients who withdraw from the study in Part A, including those who received prohibited concomitant medications, will not be eligible to participate in Part B. Subject inclusion and exclusion criteria for Part A can be found in Sections 5.1 and 5.2 of the protocol.

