4.1. Full Analysis Set (FAS)

The Full Analysis Set is defined as all subjects who enroll into the Part B study and receive at least 1 dose (including partial dose) of study drug. The Full Analysis Set is synonymous with the Intent-to-Treat Population described in the protocol.

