5.1.1. Definitions

Study Day

Study Day is defined as days relative to the date of first dose of BIVV009 in Part A, Day 0. The start/stop day of events will be calculated as (date of event – date of Day 0 +1).

Incomplete dates will be imputed for the calculation of study days, unless specified otherwise:

- If missing day only, the start date will be imputed as the first day of the month, while the end date will be imputed as the last day of the month;
- If missing day and month, the start date will be imputed as the first day of the year, while the end date will be imputed as the last day of the year;

Baseline

Baseline is defined as the last non-missing value prior to the first administration of study drug in Part A. If a transfusion occurred during the screening period, the baseline measure must be at least 7 days after the transfusion.

Study Treatment Period

For subjects who enroll into Part B, the Part A study treatment period starts at the date of first study drug administration and ends at the date of Week 26 visit. The Part B study treatment period starts following completion of Part A (ie, immediately following Week 26 visit) and ends at the ET/EOS/Safety follow-up visit, which is 9 weeks after each subjects' last dose.

The Combined Study Period includes all visits in Part A and Part B and will be utilized for a subset of analyses in order to support regulatory submissions and/or publications.

Visit Windows

Analysis by study visit will utilize the data recorded on the corresponding nominal visit from electronic Case Report Forms (eCRFs). In case of missing data/assessments for a visit, data from an unscheduled visit, or ET/Safety Follow-up Visit will be used, if the Study Day of such a

visit fits in the analytic window defined below. If multiple values are identified within the analytic window, the one closest to the target study day will be used.

- Starting at Week 27 and every 2 weeks thereafter, analytic visit windows in Part B will be -6 days to +7 days from the Target Study Days of the protocol-defined visits. An example of the first few visits in Part B can be seen in Table 1, below.

Table 1: Analytic Visit Windows

Visit	Target Study Day	Analytic Visit Window (Study Day)
Week 27	189	183-196
Week 29	203	197-210
Week 31	217	211-224
Week 33	231	225-238
Etc.		

Solicited Symptomatic Anemia

Refer to the Part A SAP for definitions regarding the severity of CAD symptomatic anemia.

Thromboembolic Events

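### Neither SAP delivers the all-dosed ADA percentage that the protocol promises, the Part B SAP still plans a 1-year Part B, and its combined-period transfusion displays are conditional on entering Part B

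*SAP*

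**What the plan says.** **Population.** Part B SAP section 7.3 covers hemoglobin, total bilirubin, transfusion numbers and rates, and time to first transfusion: "All analyses below will be conducted on the FAS for the Combined Study Period starting at Baseline/Day 0". Section 4.1 fixes the set: "The Full Analysis Set is defined as all subjects who enroll into the Part B study and receive at least 1 dose". Section 5.1.1 defines the Part A segment for the same patients only: "For subjects who enroll into Part B, the Part A study treatment period starts at the date of first study drug administration". It adds that the Combined Study Period "will be utilized for a subset of analyses in order to support regulatory submissions and/or publications". Section 3.1.1 says who is left out: "Patients who withdraw from the study in Part A, including those who received prohibited concomitant medications, will not be eligible to participate". Protocol section 5.3 agrees: "Patients who withdraw from study after Week 5 and prior to Week 23 will not be eligible to participate in Part B". Protocol section 4.1 adds that "patients requiring other treatment for their CAgD in Part A will be withdrawn from the study and counted as non-responders". The same section also contains the main limit on the effect: "Patients who receive a transfusion during Part A will not be withdrawn from the study and will be eligible to participate in Part B".

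**ADA.** Protocol section 7.7.1 defines a Part A ADA population of all dosed patients with an evaluable sample. Section 7.8.2 promises the number and percentage positive. Section 7.7.2 leaves the method to the SAP, and section 7 gives the SAP precedence. Part A SAP section 8.2.3 evaluates early discontinuers and gives a listing; its table list has no ADA table. Part B SAP section 8.2.3 summarizes incidence and prevalence for the Combined Study Period and names baseline and the ET/EOS/safety follow-up visit. It states no population, so the section 8 default applies: patients dosed in Part B (section 4.2). Neither SAP defines an ADA set.

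**Horizon.** Part B SAP sections 1, 3.1, 3.1.2 and 3.1.3 end the study 12 months after last patient out of Part A. Protocol sections 4.4 and 4.5 say 24 months, with 2 to 3 years of Part B dosing per patient. Part B SAP sections 7.2.1 to 7.2.3 and 7.3.1 summarize to Week 77 and list later data. Section 7.3.2 displays time to first transfusion only to Day 539. Section 5.1.3 makes by-visit efficacy summaries beyond 12 months optional.

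**The concern.** An analysis whose clock starts at Part A Day 0 but whose members are chosen by a later event, being dosed in Part B, leaves out the Part A experience of everyone who stopped. For transfusions the Part A SAP provides a backstop. For ADA no SAP table does. Protocol section 5.3 also names clinically significant hematologic breakthrough attributable to ADA as a possible ground for withdrawal, so the patients left out may be the informative ones.

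The second problem is a mismatch between two current documents. Because the SAP overrides the protocol where they differ on analysis, its Week 77 limit governs until corrected. Several endpoints that bear on durability, the secondary objective of Part B, would then exist only as listings for half or more of Part B calendar time.

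**Working it through.** **1. The plan's own figure.** Week 77 is 77 × 7 = Day 539, Study Day 540. This agrees with Part B SAP section 7.3.2.

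**2. ADA.** Inputs: N = 20 planned (protocol section 7.10). The number of Part A withdrawals is not given, so d is assumed. All 20 are assumed to have an evaluable sample, with no positives among Part B entrants.

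- d = 1, and that patient positive: all dosed 1/20 = 5.0% (Clopper-Pearson 95% CI 0.1–24.9%); Part B set 0/19 = 0% (0–17.6%).
- d = 2: Part B set 0/18 = 0%; all dosed 0 to 2/20 = 10%.
- d = 4: Part B set 0/16 = 0%; all dosed 0 to 4/20 = 20%.

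Time points: protocol section 4.3.8 samples every 3 months in year 1 of Part B and every 6 months after that. This gives 4 + 2 = 6 on-treatment samples over 2 years and 4 + 2 + 2 = 8 over 3 years, if amendment 06 applied throughout. There are fewer where earlier testing depended on consented PD back-up samples. Part B SAP section 8.2.3 names none of these and does not exclude them, so which samples define incidence is open.

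**3. Horizon.** Part B starts at Week 27; 2 years end at about Week 131 and 3 years at about Week 183.

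| After Week 77 | 2-year Part B | 3-year Part B |
|---|---|---|
| Calendar time | (131−77)/(131−27) = 54/104 = 52% | (183−77)/(183−27) = 106/156 = 68% |
| Two-weekly symptomatic anemia | 27/53 = 51% | 53/79 = 67% |
| LDH, haptoglobin (four-weekly from Week 79) | 14/40 = 35% | 27/53 = 51% |
| Quarterly PROs | 4/8 = 50% | 8/12 = 67% |

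Counts use the on-site schedule: 26 two-weekly visits in Weeks 27–77, 53 to Week 131, 79 to Week 183. Four-weekly panels from Week 79 number 14 to Week 131 and 27 to Week 183.

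**4. Transfusions.** Assumptions: N = 20, c continuing patients transfused, k withdrawals after Week 5, j of them transfused first. Withdrawals before Week 5 have no time at risk.

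- Part B set, transfusion-free: (20−k−c)/(20−k).
- All dosed, Kaplan-Meier: (20−c−j)/20 if transfusion-free withdrawals are censored after all events; (20−k−c)/(20−(k−j)) if before any event.

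| c | k | j | Part B set | All dosed | Difference (points) |
|---|---|---|---|---|---|
| 2 | 0 | 0 | 90.0% | 90.0% | 0 |
| 2 | 1 | 0 | 89.5% | 89.5–90.0% | −0.5 to 0 |
| 2 | 1 | 1 | 89.5% | 85.0% | +4.5 |
| 2 | 2 | 0 | 88.9% | 88.9–90.0% | −1.1 to 0 |
| 2 | 2 | 1 | 88.9% | 84.2–85.0% | +3.9 to +4.7 |
| 2 | 2 | 2 | 88.9% | 80.0% | +8.9 |
| 6 | 1 | 0 | 68.4% | 68.4–70.0% | −1.6 to 0 |
| 6 | 1 | 1 | 68.4% | 65.0% | +3.4 |

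**The case against.** The Part B population is not a departure from the protocol. Protocol section 7.4.1 defines the Part B FAS the same way, and section 7 says that the two parts are analyzed and reported separately. No Part B hypothesis is tested. All-dosed transfusion number and time to first transfusion are already in Part A SAP sections 7.3.4 and 7.4.1.3, within Part A. This stands, and it reduces the transfusion point to labeling or a supportive analysis.

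A reader might infer that the combined transfusion results must flatter the drug. The documents do not support that. Transfusion does not bar Part B entry, the number of withdrawals is not given, and the sign depends on whether those who left had been transfused.

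A reader might also infer that no document provides for an all-dosed ADA percentage. Protocol sections 7.7.1 and 7.8.2 do; the gap is that neither SAP carries it out. The ADA-positive withdrawal would be visible in the Part A listing, and the two intervals in the example overlap widely. Both points are fair, but a listing is not the promised percentage.

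On the horizon, section 5.1.3 gives varying treatment duration as the reason for the 12-month limit, and allows later summaries depending on how many subjects attend. Under a 1-year plan 12 months was roughly the minimum follow-up; under the current protocol the minimum is about 2 years, so that reason no longer supports Week 77. The time-to-transfusion calculation uses all data; only the display is cut.

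The stronger reading, that durability cannot be assessed after Week 77, fails. Hemoglobin, total bilirubin and reticulocytes are summarized to the end of Part B as safety laboratory data (sections 8.2.1 and 8.2.1.1). Annualized transfusions, hemolytic breakthrough, thromboembolic events and AEs are also covered (sections 7.3.1, 7.2.2 and 5.1.3). LDH and haptoglobin are not in the section 8.2.1 chemistry list, so they are not rescued this way.

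**Conclusion.** The concern holds on three points of unequal weight.

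1. **ADA:** the percentage that the protocol promises is produced by neither SAP on all dosed patients. One ADA-positive Part A withdrawal would turn 5% into 0%. This assumes N = 20, all evaluable and no other positives; with no such withdrawal there is no numerical effect on the count of positives.
2. **Horizon:** 12 against 24 months is a plain conflict between current documents. For the Week-77-limited endpoints, 52% to 68% of Part B calendar time, and 35% to 67% of scheduled assessments depending on the endpoint, has no committed summary. The durability objective is only partly affected.
3. **Transfusions:** the combined displays condition on Part B entry. In the cases shown the effect runs from −1.6 to +8.9 points and is zero without Part A withdrawals. This is a matter of interpretation and labeling, not a demonstrated bias.

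The Part B SAP still refers to an intent-to-treat population in the protocol, so it probably predates amendment 06, which added both the second year and routine Part B ADA sampling. That is an inference: its date and base protocol version are not visible in the text available. Points 1 and 2 should be corrected. Confidence is medium, because Part A withdrawals are not given.

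**What to change.** 1. **ADA.** Define an ADA analysis set of all patients dosed in Part A with at least one evaluable sample. Report combined incidence and prevalence on it. State that all available on-treatment samples count, including any tested PD back-up samples, as well as baseline and ET/EOS.
2. **Horizon.** Update the Part B SAP to 24 months after last patient out. Commit the Week-77-limited summaries and the Kaplan-Meier display to the end of Part B, with n or number at risk at each time.
3. **Transfusions.** Label the Combined Study Period displays as conditional on Part B entry, or add a supportive all-dosed version using observed data for withdrawals, as Part A SAP section 7.3.4 does. If early withdrawals are added, report transfusions per total patient-years. Individual annualized values from short follow-up are inflated: 2 transfusions in 90 days gives 2/90 × 365.25 = 8.1 per year. Under the current plan so short a combined denominator would not normally arise, because every Part B entrant contributes Part A through Week 26.

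The cost is a SAP amendment and longer tables with small n at late visits. No new visits are needed. ADA testing of back-up samples remains subject to consent.
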